C.4.a. Inclusion Criteria. *Therapists:* 1) Treat child anxiety patients; 2) Current license as a mental health professional (e.g., psychologist, clinical social worker, marriage and family therapist, professional counselor); and 3) competence to provide therapy to youth based on review of institutional or state licensing records. *Patients:* 1) Youth between the ages of 7 and 17 presenting for outpatient therapy with a principal diagnosis of social phobia, separation anxiety disorder, panic disorder with and without agoraphobia, specific phobia, or obsessive compulsive disorder (based on structured interview, additional available information and consensus of [name] and evaluator); 2) A parent or other primary care giver available to participate with the child in all assessment and treatment activities; and 3) English speaking.

C.4.b. Exclusion Criteria. *Therapists:* 1) History of investigation or disciplinary action (based on review of institutional records), Trials 2 and 3 only; and 2) Opposition to CBT per survey responses. *Patients:* 1) History of and/or current diagnoses of: psychosis, autism, bipolar disorder, mental retardation, oppositional defiant disorder, selective mutism, PTSD, or major depressive disorder measured by structured interview and all available clinical information; 2) current suicidality as assessed by the depression module of the structured diagnostic interview and the CDI-S; 3) A positive diagnosis in the caregiver of mental retardation, psychosis, or other psychiatric disorders or conditions limiting their ability to understand CBT (based on clinical interview); 4) an adequate trial of CBT for the child of any psychiatric disorder based on clinical interview; and 5) Initiation or dose change of an antidepressant for the child within 8 weeks or an antipsychotic within 6 weeks of enrollment. Patients and their prescribers will be encouraged to refrain from changing psychotropic medications or dosages during the study without consulting the study staff (Human Subjects); changes will be recorded and analyzed.

C.5. Interventions. Each therapist will be randomized to treat one or two patients with TAU or FTF-AC. The general intervention structure is consistent across treatments to avoid confounding variations.

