C.5.a. General Intervention Structure. In Trial 2, prior to each patient beginning treatment an intervention specialist will conduct a 30 to 90-minute training session with the therapist via phone and provide an electronic version of the protocol. Before the training with the intervention specialists, therapists providing treatment with AC therapists will have an additional phone call with the study coordinator to receive assistance accessing the

technology, In each condition the therapist will provide 6 to 12 treatment contacts over the 12-week period. These parameters are based on the median and modal number of sessions attended by patients in the our clinic (6)⁷⁷ and the number of sessions in the seminal trial of childhood anxiety treatment (12).³⁰ The frequency of these session is expected to be weekly for approximately the first month and then can be based on therapist's clinical judgment. These requirements are to ensure that patients receive a sufficient treatment dose to compare therapist behavior across conditions. In each condition of Trial 2 an intervention specialist will: 1) Review each patient weekly; 2) respond to therapist inquires within 24 hours; and 3) contact therapists not adhering to the protocol. In Trial 1 the therapists will be able to contact an intervention specialist over with question about how to use Anxiety Coach for a six-month period following the initial training.

C.5.b. Treatment as Usual (TAU). In the TAU condition (Trial 2) therapists provide treatment consistent with their orientation and clinical judgment. Previous research suggest that TAU will include supportive therapy, relaxation, and cognitive restructuring.¹⁵ The format of treatment will be 6 to 12 50-minute face-to-face therapy sessions in the therapist's office, with flexibility to leave the office (e.g., for exposure). Therapists can communicate with patients between sessions (e.g., phone calls), as long as this medium is not the primary mode of treatment. In preparation for TAU the project director will train therapists in: 1) teaching patients and caregivers to record daily symptoms with the iPod Touch; 2) audio recording sessions; 3) the role of the project director to track progress and provide support; and 4) the guidelines regarding the structure of sessions.

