C.7.a. Therapist Survey. A survey will be sent to all the mental health providers contracted by MMSI under IRB 14-002608. Therapists that practice in areas designated by the U.S. Department of Health and Human Services as Mental Health Care Health Professional Shortage Areas,⁷⁸ treat children with anxiety disorders, endorse openness to CBT, and report infrequent use of exposure will be recruited into the study.

C.7.b. Therapist Telephone Screening and Consent. Therapist eligibility and interest in participating in the study will be assessed through phone screening completed by the study team. Information regarding licensure status, frequency of treating children with anxiety disorders, and openness to piloting a smartphone-based CBT aide will be confirmed by the therapists' institution. Therapists that meet inclusion/exclusion criteria will be mailed a consent form.

C.7.c. Patient Telephone Screening. For Trials 2 and 3, a multi-gate screening procedure will be used to recruit patients. Interested patients evaluated as part of clinical practice by participating therapists will be an informational letter, instructions, two copies of the consent/assent documents, parent- and child-report forms, and instructions to contact the study team for pre-consent screening. Therapists will also relay patient name and information to study staff via telephone for contact. During the screening call, information regarding the

patient's symptoms, previous treatment and diagnoses, and willingness to be assigned to one of three treatment conditions will be gathered. The number of callers deemed ineligible and reasons for ineligibility will be recorded in the Screening Log. If patient is likely to be eligible, a consent and evaluation videophone visit will be scheduled. This visit should occur within 1 week (+/- 1 week) from the initial therapist visit.

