If therapists in Trial 1 choose to use Anxiety Coach in their practice during, those patients will not be engaged in any research activities. In order to use the application the patient must agree to the terms of use that explain what data Mayo Clinic collects and how these data are used.

C.7.e. Treatment Assignment. For Trial 2, therapists will be randomized to either TAU or FTF-AC after they are consented. The therapist will then offer participation to the next patient they see likely to qualify. (If needed, the second patient treated by a therapist randomized to TAU will be enrolled in the FTF-AC condition.) This format clearly differentiates the therapists' participation in the study from the patients' participation. To limit bias in enrollment, neither patients nor the independent evaluators will be aware of therapeutic condition at the time of enrollment. Treatment in each condition can begin within 1 to 2 weeks of the evaluation as soon as the patient has completed the study evaluation. All patients will be informed that participation in the study includes the possibility of enrollment into either of two conditions. If patients discontinue treatment prematurely, before the sixth session, they will not be replaced with another patient. Instead efforts will be made to complete early withdrawal post-treatment evaluations on all enrollees and the frequency of premature discontinuation will be compared between conditions. For Trial 1, the therapists will have access to the Anxiety Coach application and can use it as they choose in their clinical practice. For Trial 3, treatment assignment will occur following consent and the pre-evaluation is completed.

C.7.f. Therapists, Treatment Integrity and Competence. Therapists in Trials 2 and 3 will provide treatment. To determine the success of creating conditions with distinct therapist behavior, all sessions and communication in each condition will be recorded and coded for use of exposure and other interventions. In the TAU condition, the therapist will not receive any instruction regarding the content of treatment. In all three conditions across the two trials the intervention specialists or the PI will monitor and support the therapists' compliance with guidelines. The intervention specialists have highly developed therapeutic skills, at least five years' experience providing CBT to children with anxiety disorders and their families, extensive one-on-one

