Patients (children and caregivers) will be recruited for participation in the study by the enrolled therapists. During the initial evaluation the therapist will describe the study including its voluntary nature using a prepared script. The therapists will provide families that express interest in participation a study packet and encourage them to contact study staff to schedule screening visit. The study coordinator will conduct a phone screening with the caregiver including questions to assess the presence of an anxiety disorder and obtain other information relevant to inclusion and exclusion criteria (e.g., diagnostic and treatment history). Those who are determined to be ineligible will be offered other treatment options including treatment with the referring therapist, an evaluation at Mayo Clinic outside of the study if appropriate, and resources for finding other providers. Those who appear to be eligible will be scheduled for the videophone Consent and Evaluation visit. During the initial part of this visit, the patient and parents will be given a review of the informed consent document including information about the treatment options within the study, potential risks and benefits of study participation, as well as any alternatives to participating in research. The investigators will try to foster an open exchange of information and will encourage the child and caregivers to ask questions and discuss concerns. It will be the responsibility of [name] to ensure that all participants (therapists, patients, and caregivers) have provided consent/assent and understand their role in the research. Participants will be told that they can discontinue participation at any time, or refuse to answer any study questions, without adverse consequences. If patients and caregivers are interested in participation, a copy of the consent and assent documents will be signed and placed in the postage-paid envelope included with the study packet. To minimize delay in beginning therapeutic treatment, the pre-treatment evaluation will be conducted at this visit. However, patients will not be considered to be enrolled in the study until the signed consent/assent documents have been received and signed by study staff. In the event that data is collected but signed consent/assent documents are not received, data will be excluded from any research-related activities or analyses. Data on screening, eligibility decisions, and enrollment will be tracked.

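### In Trial 2 the arm is fixed before the child is screened, but enrollment masking leaves out the phone screener and the person who shares the diagnostic consensus

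*Protocol*

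**What the plan says.** **Order of events (Protocol C.7.e).** "For Trial 2, therapists will be randomized to either TAU or FTF-AC after they are consented". After that: "The therapist will then offer participation to the next patient they see likely to qualify". A TAU therapist's further child also has an arm set in advance: "If needed, the second patient treated by a therapist randomized to TAU will be enrolled in the FTF-AC condition". In Trial 3, by contrast, assignment follows consent and the pre-treatment evaluation.

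**Masking at enrollment (C.7.e).** "To limit bias in enrollment, neither patients nor the independent evaluators will be aware of therapeutic condition at the time of enrollment". No other role is named.

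**Phone screen (4.1.2.a and C.7.c).** "The study coordinator will conduct a phone screening with the caregiver including questions to assess the presence of an anxiety disorder". The call acts as a gate: "If patient is likely to be eligible, a consent and evaluation videophone visit will be scheduled". C.7.c also has therapists telephone the family's details to study staff, and has the count of ineligible callers and the reasons entered in a Screening Log. Section 4.1.2.a adds that screening, eligibility and enrollment data are tracked.

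**The coordinator's other duty (C.5.a).** For those treating with Anxiety Coach, "therapists will have an additional phone call with the study coordinator to receive assistance accessing the" technology. This call comes before the intervention specialist's training session, which in turn precedes each patient's treatment.

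**Diagnosis for inclusion (C.4.a).** The principal diagnosis is "based on structured interview, additional available information and consensus of [name] and evaluator".

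**Formal decision (C.7.d).** Eligibility is formally settled by an independent evaluator who is blind to condition.

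**The plan's own claim (C.6.a).** Randomizing therapists or patients is said to do away with any scope for bias in recruitment.

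**The concern.** When allocation exists before a participant is screened, anyone who both knows it and helps decide who enters can let through different children in each arm, without intending to. C.7.e recognizes this risk and masks two groups against it. Two study-side decision makers fall outside that sentence: the coordinator at the phone screen, and the person who agrees the diagnosis with the evaluator. The phone screen calls for judgment about likely eligibility, and the diagnosis may draw on information beyond the structured interview.

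If borderline children were passed or failed differently by arm, the arms would differ at baseline. The Trial 2 comparison of symptom change (C.10.b.2) and the feasibility figures on screening yield would carry that difference forward. C.10.b.2 says these comparisons are meant to produce effect estimates for planning a fully powered trial, so a distorted estimate matters even if no test is relied upon.

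**Working it through.** The plan gives no figure to reproduce: no screen-failure rate, power or effect size. The check is therefore mainly a trace of who can know the arm at each step, followed by an illustration of size.

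**Trace**

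1. *Therapist randomized, then child approached (C.7.e).* The arm is known to the therapist and to staff who hold the allocation.
2. *Referral to study staff (C.7.c).* The child is linked to a therapist. The therapist's name reveals the arm only to someone who knows the allocation.
3. *Phone screen by the coordinator (4.1.2.a, C.7.c).* No masking is stated. C.5.a gives the same role a call made only to Anxiety Coach therapists. That call is tied to training before each patient's treatment and is not placed before or after the child's screen. For a therapist's first child it may follow the screen. C.5 allows one or two patients per therapist, so before an Anxiety Coach therapist's second child is screened, the call for the first would normally have been made.
4. *Evaluation (C.7.d).* The evaluator is blinded, but sees only children who passed step 3.
5. *Diagnostic consensus (C.4.a).* The evaluator and one other person, for whom no masking is stated and whose knowledge of the arm is not stated either.

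**Illustration of size**

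From the documents: 30 therapists and 30 children in Trial 2 (protocol, Trial 2 description). Assumed: 1:1 allocation, so 15 per arm; severity standard normal; a share q of referrals removed in one arm only, being those who seem most complex at screening; correlation ρ = 0.5 between that impression and baseline severity; pre-post correlation r = 0.5; no treatment effect.

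- Baseline shift in the filtered arm = ρ·φ(z)/(1−q), where z is the normal quantile at 1−q.
- Bias in the between-arm difference in change = (1−r) × baseline shift.
- SD of change = √(2(1−r)) = √(2 × 0.5) = 1. The standard error of the difference in change is then √(2/15) = 0.365, the same as for a baseline difference.

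| q | φ(z)/(1−q) | Baseline shift (× 0.5) | Bias in change (× 0.5 again) | Bias ÷ 0.365 |
|---|---|---|---|---|
| 10% | 0.195 | 0.10 SD | 0.05 SD | 13% |
| 20% | 0.350 | 0.175 SD | 0.09 SD | 24% |
| 30% | 0.497 | 0.25 SD | 0.12 SD | 34% |

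The result depends on ρ. If the impression tracked severity perfectly (ρ = 1), the baseline shifts would double to 0.20, 0.35 and 0.50 SD. Even then a two-sided 5% test of baseline severity would flag them in only about 8%, 16% and 27% of trials. A baseline table is thus a weak check, which is why exclusion counts by arm are more useful.

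**The case against.** The strongest reply is that the decision that counts is already protected. C.7.d gives formal eligibility to a blinded evaluator, and under C.4.a the other consensus member cannot settle the diagnosis alone. The phone screen is preliminary, and exclusions and their reasons are logged. This stands as real mitigation. It does not close the gap, because the evaluator never sees a child stopped at the phone screen.

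A second reply is that the recruiting therapist knows the arm and chooses whom to approach, which is probably the larger route and is untouched by masking staff. That is also right. It limits what the remedy can achieve, but it is no reason to leave the other route open.

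A third is that the study is unpowered and mainly descriptive (C.10.a), its group tests are exploratory (C.10.b.2), and the SAP names no between-group test. This stands and keeps the point minor.

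A reader might infer four stronger things that the documents do not support:

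- *That the coordinator knows the arm at every screen.* The timing of the technology call is not stated, so knowledge is clear only for later children.
- *That the consensus member knows the arm.* Nothing shows this; only the absence of stated masking can be shown.
- *That the therapist's name gives away every child's arm.* It does so only to someone who knows the allocation, and a TAU therapist's second child may be treated with Anxiety Coach.
- *That such selection could not be detected.* The Screening Log would hold a trace, although the plan does not say it will be reported by arm.

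**Conclusion.** The masking gap is real but minor. In Trial 2 the arm precedes screening, the enrollment masking sentence omits the phone screener and the consensus member, and the screener's role has a documented route to the arm, at least for later children of Anxiety Coach therapists. The claim in C.6.a is therefore stronger than the procedures allow. Nothing shows that differential selection occurred.

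The size of any bias is unknown. The range of about 0.05 to 0.12 SD in change rests wholly on assumed exclusion rates, an assumed direction and two assumed correlations of 0.5. It amounts to roughly 13% to 34% of one standard error at 15 per arm, itself an assumption of equal allocation. The reason to act is that the remedy is cheap, not that the estimate is badly compromised. Trial 3 does not share the problem.

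**What to change.** 1. In C.7.e, extend masking to the person doing the phone screen until the eligibility decision is recorded, and to the consensus member where existing staffing allows. If the latter is not possible, say so.
2. In C.5.a, give the technology call to the intervention specialist, who already trains the same therapist.
3. In C.7.c, have an existing unmasked staff member other than the screener take the therapist's referral call and pass the family on without therapist or arm. Coded referrals alone would not work with the present telephone handover.
4. Tabulate referrals, exclusions and reasons from the Screening Log by therapist arm.
5. Qualify C.6.a: randomization does not by itself remove recruitment bias here, because the recruiting therapist remains unmasked.

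The cost is some protocol wording, one reassigned call and a little more coordination at referral handover, using existing roles and data. Items 4 and 5 remain useful even if Trial 2 enrollment has closed.

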supervision from [name], attendance of workshops on anxiety treatment, and been involved in the development of *Anxiety Coach*. [name] will train the intervention specialists in the procedures outlined in the UPM for supporting therapists, meet weekly for supervision, and provide additional supervision as needed for concerns about a therapist's use of the study interventions or a patient's progress, clinical deterioration, or development of new symptoms.

C.7.g. Assessment Timeline. Patient participants will receive two assessments conducted via videophone by a trained independent evaluator blind to condition under the supervision of [name]. The initial assessment will be conducted at baseline (Time 1) when the patient's eligibility is determined. The patient will begin treatment within one to two weeks. The patient's response to treatment will be assessed 12 weeks (+/- 2 weeks) after the initial treatment session (Time 2). The evaluations will be comprehensive in nature (e.g., diagnostic interview, clinician ratings, parent- and self-reports). Accommodations will be made for families without electronic access, such as videophone assessments in the therapist's office. Beginning at the baseline assessment and continuing throughout the study, patients will rate their daily symptoms with an iPod Touch. Therapists in Trial 1 will complete the survey materials from Phase I inquiring about treatment practices and beliefs prior to receiving training in the use of *Anxiety Coach*. Two weeks after receiving *Anxiety Coach* training the therapists will be asked to complete the same survey material plus measures assessing software usability. 6 months after the initial training, therapist will be asked to complete the survey material, usability measure, and a questionnaire about their actual use of *Anxiety Coach* since the training.

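### In Trial 3, Time 2 is dated from the first treatment session, which follows assignment, so a late start moves the outcome visit and a control who never starts has no visit date

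*Protocol*

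**What the plan says.** C.7.g (Assessment Timeline) sets one schedule for all patient participants. Time 1 is the baseline evaluation at which eligibility is settled. Then "The patient will begin treatment within one to two weeks", and response "will be assessed 12 weeks (+/- 2 weeks) after the initial treatment session (Time 2"). Neither the protocol nor the SAP gives Trial 3 a different visit window.

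On the order of events, C.7.e (Treatment Assignment) states: "For Trial 3, treatment assignment will occur following consent and the pre-evaluation is completed". The first session of the assigned treatment therefore comes after assignment. The same section says "Treatment in each condition can begin within 1 to 2 weeks of the evaluation". For patients who stop before the sixth session it adds that "efforts will be made to complete early withdrawal post-treatment evaluations on all enrollees".

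Three sections describe treatment of Trial 3 controls:

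- C.3.b (Trial 3): usual care in the community or within Mayo Clinic, but not from the current therapist.
- C.5.e: the existing services of the therapist over a 12-week period whose starting point is not given. Release of outside records is requested after 12 weeks.
- C.8.d: guidelines for both Trial 2 and Trial 3 tell the therapist to interact weekly for 6 to 12 weeks.

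MC-AC is delivered by study staff (C.3.b, C.5.d).

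The principal analysis set is intention to treat (C.10.c), and 4.1.2.b says that all randomized participants will be analysed. C.10.b.2 plans a between-group repeated-measures analysis of variance of symptom change in Trial 3. It calls the group tests exploratory and says the work is meant to help plan a fully powered trial. The SAP is mainly descriptive.

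**The concern.** The clock for the outcome visit starts at an event that happens after assignment and that the two arms reach by different routes. Study staff can book the first MC-AC session themselves. Under C.3.b, a control has to begin with a different provider. If that takes longer, the control's Time 2 comes later after Time 1 than an MC-AC child's, yet the analysis treats both as the same post-treatment point. The +/- 2 week window does not absorb this, because it moves with the first session.

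For a control who never has a first session, the C.7.g rule produces no date. That sits badly with an intention-to-treat set. C.10.c would then fall back on complete cases or last rank carried forward, with mean, median, worst-case and best-case imputation as sensitivity analyses. Daily ratings continue from baseline ("patients will rate their daily symptoms with an iPod Touch"), but they do not replace the blinded Time 2 evaluation.

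Trial 3 carries the label Increasing Access. Delay in reaching usual care is part of what assignment does there, and dating Time 2 from the first session takes that delay out of the comparison.

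**Working it through.** The plan states no Time 1 to Time 2 interval, so it has to be derived.

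**Inputs.** Time 2 is at 12 +/- 2 weeks after the first session (C.7.g). The planned start is one to two weeks after the evaluation (C.7.g, C.7.e). Trial 3 has 30 patients (Specific Aims, Aim 2); the allocation ratio is not stated. No control start delay or non-start rate is given.

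**Formula.** With s = weeks from Time 1 to first session, Time 2 falls at s + 10 to s + 14 weeks after Time 1, nominally s + 12.

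**On plan.** s = 1 gives 11 to 15 (nominal 13), and s = 2 gives 12 to 16 (nominal 14). Together that is 11 to 16 weeks, with nominal dates at most one week apart. If an immediate start is allowed, s = 0 gives 10 as the lower end.

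**Late control start (assumed values of s).** The gap is the control's nominal date minus the MC-AC nominal date of 14 (start at week 2) or 13 (start at week 1).

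| Control start s | Time 2 window, weeks from Time 1 | Nominal | Gap to MC-AC |
|---|---|---|---|
| 4 | 14 to 18 | 16 | 2 to 3 weeks |
| 6 | 16 to 20 | 18 | 4 to 5 weeks |
| 8 | 18 to 22 | 20 | 6 to 7 weeks |

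The nominal date passes the on-plan maximum of 16 weeks once s exceeds 4 (s + 12 > 16). The whole window passes it once s exceeds 6 (s + 10 > 16).

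**No start.** s is undefined, so C.7.g gives no date. If the 30 patients split 15/15 (an assumption), each control without Time 2 is 1/15 = 6.7% of the arm.

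**Do other passages supply the date?**

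- The C.7.e promise of evaluations is worded around early discontinuation and carries no date.
- The 12-week period in C.5.e has no stated origin.
- C.7.f says that in all conditions "the intervention specialists or the PI will monitor and support" therapists' compliance with guidelines, but it sets no start deadline.
- The explicit duty to contact non-adhering therapists is written for Trial 2 (C.5.a: "In each condition of Trial 2 an intervention specialist will: 1) Review each patient weekly").
- Weekly review under 4.1.5 would notice a non-start but would not fix a visit date.

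**Under a fixed rule of 14 +/- 2 weeks from Time 1.** Time 2 falls at 12 to 16 weeks for everyone. Time since first session is 12 - s to 16 - s: 11 to 15 weeks for s = 1, 10 to 14 for s = 2, 8 to 12 for s = 4, 6 to 10 for s = 6, and 4 to 8 for s = 8.

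**The case against.** The strongest reply is that harm needs a departure from the stated plan. Both arms are expected to start within one to two weeks, and if they do, the nominal dates differ by at most a week. That stands, and the late starts above are assumptions.

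Second, the route to delay depends on C.3.b. Under C.5.e, controls use services the therapist already offers. C.7.c and C.7.d have families recruited after an evaluation by a participating therapist, and C.8.c says only patients with access to services are included. If C.5.e governs, long delays are much less likely. That also stands, and it is why the conflict over who treats controls should be settled first.

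Third, C.7.g describes Time 2 as measuring response to treatment, and dating it from the first session holds treated time roughly constant. That is a legitimate target, but it fits poorly with intention to treat and cannot cover a patient who is never treated.

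A reader might go further and infer that controls will be assessed later, that never-starters will go unevaluated, or that Trial 3 is biased in a known direction. The documents support none of these. They give no delay or non-start rate, the same rule applies to both arms, C.7.e intends evaluations for all enrollees, and weekly review would bring a non-start to light. What is missing is a date.

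**Conclusion.** The point holds in a limited form. In Trial 3 the timing of the outcome visit depends on a post-assignment event, and C.7.g gives no date for a patient without a first session. On plan the effect is negligible. Off plan each week of control delay moves Time 2 by one week: 2 to 3, 4 to 5 or 6 to 7 weeks beyond an on-plan MC-AC child for assumed starts at week 4, 6 or 8. These figures rest on assumed delays and on reading C.3.b as governing where controls are treated. Because the study is unpowered and the comparisons exploratory, what is affected is the comparability of pilot estimates intended to help plan a full trial, not a confirmatory test. The direction and size of any bias cannot be established from the documents. This is a cheap improvement of low to moderate severity.

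**What to change.** First, reconcile C.3.b, C.5.e and C.8.d on who treats Trial 3 controls and with what contact; until then it is unclear which session counts as a control's first. Then:

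- For both Trial 3 arms, schedule Time 2 at one fixed interval from Time 1, whether or not treatment has begun. For example, 14 weeks +/- 2 gives 12 to 16 weeks, inside the interval already implied.
- Give the 12-week period and the records request in C.5.e that same origin.
- Record the date of first session, or none, so that treated time can be described.
- At a minimum, apply the fixed date to any patient with no first session.

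Time 1 is a better origin than assignment. C.7.d delays enrollment until signed forms arrive, so if assignment came L weeks after Time 1, the same interval counted from assignment would give 12 + L to 16 + L weeks.

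The cost is wording in C.7.g and C.5.e plus one recorded variable. The downside is that late starters will have had less treatment by Time 2: a week-8 starter would have 4 to 8 weeks since first session, against 10 to 14 now. The estimate then describes the effect of assignment, in line with the intention-to-treat set, rather than response after a fixed treated period. It may favour MC-AC if late starts fall mainly on controls. Patients who start on plan change little. Controls receive Anxiety Coach after the post-treatment evaluation (C.7.h), so a scheduled Time 2 also gives that handover a date.
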